8 INTERVENTION DISCONTINUATION

Condition for which the study intervention (CE cream) will be discontinued:

- Intolerance of the study cream by the participant related to developing toxicity (e.g., allergy to conjugated estrogen or the vehicle in the active or placebo creams). This is determined by patient report and/or signs on physical examination, e.g. vulvovaginal skin irritation or inflammation: erythema, ulcerations, lesions, heat, tenderness, edema.

Temporary study medication discontinuation:

If symptoms or signs of vulvovaginal irritation exist but it is unclear whether this is related to study medication (e.g., vaginal discharge perhaps due to other conditions such as *Candidiasis* or bacterial vaginosis), these conditions may be treated with vaginal therapies (e.g. clotrimazole or metronidazole or clindamycin creams) at the discretion of the clinical provider. In these scenarios, *temporary discontinuation* of the study medication cream may be deemed appropriate. The study cream should be resumed as soon as reasonably appropriate clinically.

Elective study medication discontinuation by the participant:

Subjects may, of course, withdraw voluntarily from participation in the study at any time and for any reason. Participants will continue to be followed, with their permission, even if the study intervention is discontinued. There are no planned modifications to the schedule and duration of continued follow-up after study medication discontinuation.

There currently are not plans for replacement of subjects who discontinue early.

If voluntary withdrawal occurs, the subject will be asked to continue scheduled evaluations, complete an end-of-study evaluation, permit collection of a VMI specimen, and be given appropriate care under medical supervision until the symptoms of any AE resolve or the subject's condition becomes stable.

9 STATISTICAL CONSIDERATIONS

9.1 General Design Issues

A large simple trial (randomized, controlled) design was selected to evaluate for possible superiority of vaginal estrogen cream use compared to placebo. The primary outcome is a comparison by treatment group of time-to-failure of the prolapse repair at 1 year after surgery with "failure" defined by the *any* of these outcomes occurring:

- Recurrent prolapse beyond the hymen of the anterior or posterior vaginal wall *or* apical descent >1/3 into the vaginal canal based on continuous measurements of the Pelvic Organ Prolapse Quantification (POP-Q)⁷¹ examination
- Report of any symptoms of bulge: “yes” to question #3 of the Pelvic Floor Distress Inventory, “Do you usually feel a bulge or something falling out that you can see or feel in your vaginal area?” or *no change* or worse on the Patient Global Impression of Improvement (PGI-I).
- Retreatment of prolapse with either pessary or surgery

The null hypothesis for this study is that 12 months following transvaginal native tissue repair for prolapse with or without preoperative and continued postoperative local estrogen treatment, women will have the same rate of recurrent prolapse. The current definition of success in a surgical trial used by NICHD’s Pelvic Floor Disorders Network (PFDN) is this same composite of no prolapse beyond the hymen, no symptomatic recurrence, and no retreatment.^{81,82}

9.2 Sample Size and Randomization

The literature reports failure by the above definition occurring in ~40% of patients with a native tissue USLS (i.e., ~60% “success”).⁶⁹ A 2-sided logrank test with an overall sample size of **188 subjects** (94 each group) achieves 80% power at a 0.05 significance level to detect a hazard ratio of 0.5188 when the proportion of those "surviving" (i.e. "successes") in the control group is **65% compared to 80%** in the treated group, **measured at 1 year**. This presumes the accrual pattern across the study time period (3 years of accrual) is uniform. This N=188 already accounts for **25%** either lost to follow-up *or non-adherent to study cream* in the control and treatment groups. Allowing for an additional **15% loss of participants** from baseline to surgery, **222 total participants** are needed.

Potential problems & alternatives:

Differences in baseline characteristics between the groups may occur by chance, but we will mitigate that risk by stratifying by clinical site, hysterectomy status, and duration since menopause (<10y & ≥10y).

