Design: Randomized, double-blind, placebo-controlled trial of pre- and postoperative intravaginal estrogen therapy in 222 postmenopausal women with symptomatic prolapse undergoing a standardized surgical repair using native tissue.

Primary outcome: prolapse recurrence as defined by a composite of objective prolapse beyond the hymen, subjective/symptomatic prolapse (feeling of a bulge or *no change* or *worse* on the patient's global impression of improvement), or retreatment (e.g., reoperation or pessary use) assessed 1 year postoperatively. *Time to failure* will be compared in the two groups.

Important secondary outcomes assessing for changes in overactive bladder and urinary incontinence symptoms will be made by comparing symptoms (validated questionnaires) from Baseline to Pre-op/time of surgery. Aim 3 (see above, histomorphology, connective tissue studies) will be assessed from full thickness anterior apical vaginal wall biopsies taken at the time of surgery.

Interventions and Duration

Intervention: 1g conjugated estrogen (CE) cream (Premarin®, Pfizer Inc.) given nightly for 2 weeks then twice-weekly to complete planned 6-8 weeks (5 weeks minimum) therapy before a standardized uterosacral or sacrospinous ligament suspension transvaginal prolapse repair surgery. Those with a uterus will undergo concomitant total vaginal hysterectomy first. Twice-weekly CE cream application is then resumed upon discharge and continued for 1 year postoperatively.

Comparator: placebo vaginal cream, same schedule

Duration: The primary outcome of prolapse recurrence is assessed at one year postoperatively with continued surveillance of participants until 3 years postoperatively.

Sample Size and Population

Total sample size: N=222; 111 per treatment group

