1.1 Primary Objective

Determine if the experimental treatment (adjunctive vaginal estrogen given pre- and postoperatively with standardized native tissue transvaginal prolapse repair surgery) results in improved objective and patients' subjective sense of pelvic organ support, retreatment rate, postoperative satisfaction, and quality of life one year postoperatively.

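### The 80% power in Section 9.2 does not apply to the 12-month primary outcome: follow-up ending at 12 months gives at best 63-66%, and about 51-60% if the planned 25% is all loss

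*Combined protocol and SAP*

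**What the plan says.** Section 9.2 bases the sample size on a two-sided log-rank test in 188 women: "94 each group) achieves 80% power at a 0.05 significance level to detect a hazard ratio of 0.5188". The success proportions are 65% (control) and 80% (treated), measured at one year. It adds: "This presumes the accrual pattern across the study time period (3 years of accrual) is uniform". The 188 is said to include already a 25% allowance for women lost "or non-adherent to study cream". A further 15% loss before surgery takes the total to 222.

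The time point of the primary outcome is given in several places:
- Précis: "The primary outcome of prolapse recurrence is assessed at one year postoperatively with continued surveillance of participants until 3 years postoperatively".
- Section 1.1: the primary objective ends with "retreatment rate, postoperative satisfaction, and quality of life one year postoperatively".
- Section 9.1: "The primary outcome is a comparison by treatment group of time-to-failure of the prolapse repair at 1 year after surgery", and "The null hypothesis for this study is that 12 months following transvaginal native tissue repair for prolapse" the two groups have the same recurrence rate.
- Section 9.2.1: the codes are broken once every woman has reached the primary time point of one year.
- Section 9.4.1: a yes/no outcome at 12 months.

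Section 9.5 names the log-rank test and Cox regression for time-to-event data, with no date at which follow-up is censored. On treatment, the précis says: "Twice-weekly CE cream application is then resumed upon discharge and continued for 1 year postoperatively".

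**The concern.** The power of a log-rank test depends on the number of failures that enter it, and so on how long each woman is followed for that test. Section 9.2 gives success at one year but does not say that follow-up stops there. Its uniform-accrual premise matters only if women contribute follow-up of different lengths. If each woman contributes exactly 12 months, the accrual pattern has no effect on power. The power statement therefore appears to describe a longer analysis than the outcome sections define.

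Two things are at stake. A null result would be read against 80% power that the 12-month comparison does not have. And because 9.5 sets no censoring date, the choice between a 12-month analysis and a longer one could be made after the codes are broken.

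**Working it through.** **Inputs (Section 9.2):** 94 per arm; one-year success 65% v 80%, so failure 35% v 20%; two-sided 0.05; 3 years of uniform accrual; 25% lost or non-adherent.

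**Hazard ratio.** ln 0.80 / ln 0.65 = 0.2231 / 0.4308 = 0.518. The plan's 0.5188 differs immaterially.

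**Failures needed for 80% power.**
- Schoenfeld: 4(1.960 + 0.842)² / (ln 0.518)² = 72.6, so 73.
- Freedman: (1.960 + 0.842)² × [(1 + 0.518)/(1 − 0.518)]² = 77.8, so 78.

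**Reproducing the plan's 80%.** Section 9.2 does not give total duration or annual loss, so these are assumptions: constant hazards, 3 years of uniform accrual plus 1 further year, and every failure counted until the last woman reaches one year. Follow-up then runs uniformly from 1 to 4 years. With hazard h and loss rate λ, a woman's expected failure probability is h/(h+λ) × [1 − mean of e^(−(h+λ)t) over t = 1 to 4].

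| Assumed loss | Failures | Of these, after 12 months | Power (Freedman-Schoenfeld) |
|---|---|---|---|
| 22% a year | 76.3 | 30.2 | 79-82% |
| 25% a year | 73.5 | 28.2 | 78-81% |
| 141 women (188 × 0.75), no further loss | 74.2 | 35.4 | 78-81% |

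Capping each woman at 36 months changes this little: 72.3 failures with 25% annual loss (27.0 after 12 months) and 71.7 with 141 women (32.9 after), power 77-80%. Overall, 77-82% is obtained with 27-35 failures after 12 months. The 222 also reproduces: 188 / 0.85 = 221.2.

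**Follow-up ending at 12 months, no loss.** Failures = 94 × 0.35 + 94 × 0.20 = 51.7.
- Schoenfeld: Φ(½ × √51.7 × 0.658 − 1.960) = Φ(0.405) = 65.7%.
- Freedman: Φ(√51.7 × 0.3175 − 1.960) = Φ(0.323) = 62.7%.
- Two proportions (the 9.4.1 reading): Φ{[0.15√94 − 1.960√(2 × 0.275 × 0.725)] / √(0.35 × 0.65 + 0.20 × 0.80)} = Φ(0.348) = 63.6%.
- Simulated log-rank, 20,000 trials: 65.0%.

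**Follow-up ending at 12 months, the 25% taken as all loss.**
- Loss spread over the year (λ = −ln 0.75): 94 × (0.307 + 0.175) = 45.3 failures; power 57.0-60.0%.
- 25% removed outright: 141 × 0.275 = 38.8 failures; power 50.7-53.5%.

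**Every woman counted to 36 months (the full schedule).** With 25% annual loss, 82.0 failures and 82-85% power. With 22% annual loss, or 141 women without further loss, 85.5 failures and 84-86%.

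**Treated-arm failure rate detectable with 80% power against 35% at 12 months.** Set failures = n(0.35 + p) and HR = ln(1 − p)/ln 0.65, and solve for p. With 94 per arm, p = 16.8% (Freedman) to 17.7% (Schoenfeld). With 70.5 per arm (141 evaluable), p = 14.2% to 15.5%. The plan's target is 20%.

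**The case against.** The best defence is that 9.1 and the précis speak of time to failure, 9.5 names the log-rank test without a censoring date, 9.3 holds efficacy results until the end of the trial, and Aim 1 in the précis mentions annual surveillance to 3 years. A log-rank test on longer follow-up is therefore not expressly excluded. That much stands. But none of these statements makes a failure after 12 months part of the primary outcome, while the null hypothesis in 9.1 and the outcome in 9.4.1 are both set at 12 months.

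Other points also stand. The 63-66% is a best case on loss, although 9.2 plans for 25% lost or non-adherent. It also assumes a cut at exactly 12 months, whereas the visit window is 10-14 months. If every woman were followed to 14 months with no loss, constant hazards give 94 × (2 − 0.65^(14/12) − 0.80^(14/12)) = 58.7 failures and 68-71% power, still short of 80%.

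A reader might infer more than the documents support:
- That 80% is a miscalculation. It is not: it is approximately reproduced for a longer analysis.
- That 80% is the power for all planned follow-up. The full 36 months give about 82-86%; 77-82% belongs to an analysis closed when the last woman reaches one year.
- That all non-adherence dilutes the effect. The modified intention-to-treat rule keeps women in their assigned group, and Section 8 continues follow-up, with permission, after the cream is stopped. But Section 6.2.4 lets an investigator withdraw a woman who cannot adhere, so some non-adherence becomes lost information. Without the split of the 25%, no single figure for dilution can be given.

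**Conclusion.** The concern holds. For the primary outcome as the protocol defines it, power is at most 63-66% with complete 12-month follow-up and about 51-60% if the 25% is all loss, against 80% stated. A true 15-point benefit would be missed in about 34-37% of such trials with complete follow-up, or 40-49% with that loss, instead of 20%.

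The best-case figure uses 9.2's own success rates and group size, plus complete follow-up cut at 12 months. The lower range also assumes that the whole 25% is loss. The reproduced 77-82% rests on a closing date, annual loss and constant hazards that 9.2 does not state. It also needs the hazard ratio to persist after study cream has ended, because 27-35 of its failures fall after 12 months; the same condition applies to the 82-86% for full follow-up. The defect is that the power calculation and the outcome use different follow-up periods. The failure composite itself is not in question.

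**What to change.** Change wording only; no added enrolment, visits or data.

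**Section 9.2.** Restate power for the 12-month outcome, for example: With 94 women per group and success of 65% v 80% at 12 months (HR 0.518), power is about 51-60% if the 25% allowance is all loss to follow-up, and at most 63-66% with complete follow-up. Then:
- State how the 25% is divided between loss (less information) and non-adherence among women kept in the analysis (dilution).
- Give the treated-arm failure rate detectable with 80% power against 35%: about 17-18% with no loss, about 14-15.5% with 141 evaluable.
- Drop the uniform-accrual premise.

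**Section 9.5.** Name one primary test, with follow-up ending at the 12-month visit, and reconcile 9.1 (time to failure) with 9.4.1 (dichotomous).

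**If later failures were meant to count,** that is a design choice, since it changes the primary outcome. The précis, 1.1, 9.1 and 9.4.1 must then say so, and 9.2 must state the closing date, the annual loss and the assumption that the hazard ratio holds after treatment. This must be settled before the codes are broken.

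The cost of the 12-month fix is a less favourable power statement.

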Results: Demographics of Estrogen & Placebo groups were similar with no significant differences in age, BMI, parity, baseline prolapse, race/ethnicity, or route of hysterectomy. Two patients per group did not have surgery (unrelated to study medications) and were not analyzed in the final comparisons as they had no tissue biopsy. More patients in the Estrogen group (4 of 13) were non-adherent compared to Placebo (0 of 13), $P=0.030$, as assessed by a composite of patient diaries and tube weights at baseline and at surgery.

Histologic changes & collagen synthesis: Analyzed per-protocol and in those with sufficient tissue for analysis (Estrogen=8; Placebo=12), epithelial thickness was increased 1.8-fold in the Estrogen group (551 ± 45 vs. 314 ± 43 μm , $P=0.002$). Consistent with our studies in the 3 animal models,

thickness of the muscularis was increased 2.7-fold (7571 vs. 2807 μm , $P=0.088$). Levels of collagen types *1a1*, *1a2*, & *3a* mRNA were increased 6.0-, 1.8-, & 2.5-fold in the vaginal muscularis of the Estrogen group ($p<0.05$ for *1a1* & *1a2*) (Fig.1A). Immunoblot analysis was completed in 4 patients in each group with sufficient tissue for protein analysis. Collagen type Ia protein increased 9-fold in the muscularis from women treated with Estrogen ($P=0.012$) (Fig. 1B). In contrast, differences in collagen III protein were not significant ($P=0.27$). Although similar in the vaginal *mucosal* layer, total cross-linked collagen content as determined by hydroxyproline assays was increased 3.2-fold in the muscularis of Estrogen patients ($P=0.10$). These studies, therefore, indicate that collagen type I is preferentially enhanced by vaginal estrogen treatment and that the increase in collagen content is localized to the underlying fibromuscular layer.

[figure not shown]

Fig. 1. Effect of vaginal estrogen on collagen types I and III in the vaginal muscularis. A. Levels of *Coll1a1*, *1a2*, and *3a* mRNA in tissues from women treated with Placebo (n=12) or Estrogen (n=8). Immunoblot analysis (B) and densitometry (C) of collagen type I and III (n=4 per group). * $P < 0.05$; ** $P < 0.01$

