9.5 Data Analyses

Aim 1. The **primary outcome** will be analyzed according to the assigned treatment group (modified intention-to-treat): i.e., all participants that are randomized *and* undergo a surgical prolapse repair *and* have at least one postoperative assessment will be analyzed according to their randomized assignment group. All eligible subjects who consent to the study and are enrolled will be available for analysis of baseline characteristics, and those that are randomized and use their study drug will be monitored for adverse events, but they must meet the additional qualifications above (i.e., undergo surgery and have a postoperative assessment) to be analyzed for the primary study outcome. At baseline, continuous measures will be compared between groups with Student's t-test and chi-square (or Fisher's exact test) for categorical measures. Scores from repeated surveys are continuous outcomes data and will be analyzed using repeated measures analysis of variance. We will test for interactions between time effect and treatment effect. For categorical data (e.g. prolapse stage), the analysis will be by categorical data modeling using weighted least squares and mixed logit models, with cross-sectional assessments (at specific time intervals) by chi-square. For missing follow-up points there are two possible approaches: (i) if there are few missing follow-up points, then their values may be imputed through multiple imputation methods, in which case repeated measures analysis of variance may be used following multiple imputation; (ii) more likely, we will make time a random effect and a mixed effects model with repeated measures will be applied. Time-to-event or event-free-time will be analyzed using survival methods to include the log-rank test and Cox regression. For measures that may not be assumed normal, the data will be transformed using a rank transformation prior to analysis.

In accordance with NIH policy, we will include an analysis of the intervention effect (CE cream) performed by racial/ethnic subgroups, recognizing that the analyses will not have high statistical power for detecting clinically meaningful differences between races/ethnicities.

Aim 2 Outcomes. As above, continuous scores from repeated surveys will be analyzed using repeated measures analysis of variance with appropriate corrections made, as necessary, for missing data.

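### Section 9.2 sizes the trial as if women who do not use the cream leave the analysis, but the primary modified ITT analysis keeps them; its 80% power is not shown for that analysis

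*Combined protocol and SAP*

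**What the plan says.** Section 9.2 plans a two-sided logrank test with "94 each group) achieves 80% power at a 0.05 significance level to detect a hazard ratio of 0.5188", from 1-year success of 65% on placebo and 80% on CE. On timing it adds: "This presumes the accrual pattern across the study time period (3 years of accrual) is uniform". It then says that 188 has absorbed a 25% allowance, in both arms, for women either lost to follow-up "or non-adherent to study cream". It gives no split of the 25% and no reduced hazard ratio. A further 15% loss before surgery brings the total to 222.

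Sections 5.4 and 9.5 define the primary analysis set. Women who are randomised, have a prolapse repair and "have at least one postoperative assessment will be analyzed according to their randomized assignment group". Adherence is not a condition; comparisons of adherent women only are listed in Section 5.4 as per-protocol analyses. Section 8 says that women who stop the cream are still followed, with their permission, on an unchanged schedule. Section 6.2.4, however, lets the investigator withdraw a woman who cannot keep to the medication or the visits, and expects no monitoring after withdrawal.

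The documents give two figures on adherence. In the pilot (Section 2.2a), "More patients in the Estrogen group (4 of 13) were non-adherent compared to Placebo (0 of 13"). Section 2.2b cites 9.8% discontinuation over one year for twice-weekly CE cream in another trial.

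**The concern.** Loss and non-adherence act differently in an analysis by assigned group. A woman lost to follow-up takes her information with her, and dividing N by (1 − d) makes up for that. A non-adherent woman who is still assessed contributes events, but in the CE arm she moves the failure rate towards placebo. A larger N for loss does not restore a hazard ratio that has been diluted.

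If the 25% was handled as loss throughout, 80% is the power of an analysis of adherent, fully followed women rather than of the primary analysis. A null primary result would then be read against power that the plan has not shown. Adherence is a known risk here: Section 2.1 calls it poor, and Section 5.4 sets out three ways to define it.

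**Working it through.** **Inputs from Section 9.2:** two-sided α 0.05; 94 per group; 1-year success 65% v 80%; uniform accrual over 3 years; 25% allowance; 15% loss before surgery.

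**Assumptions not in Section 9.2:** constant hazards; 1 further year after accrual closes, so 1 to 4 years per woman; at first, a non-adherent CE woman fails at the placebo rate.

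**1. Reproduce the plan's figure.**
- HR = ln 0.80 / ln 0.65 = 0.2231/0.4308 = 0.518 (the plan has 0.5188).
- Event probability = 1 − [exp(−λ) − exp(−4λ)]/(3λ), which gives 0.635 on placebo, 0.417 on CE and 0.526 on average.
- Whole 25% removed: 188 × 0.75 = 141 women; 141 × 0.526 = 74.2 events.
- Schoenfeld power = Φ(√D × |ln HR|/2 − 1.96) = Φ(√74.2 × 0.658/2 − 1.96) = 80.9%. The Lakatos method gives N = 188 at 80.0%.
- 188/0.85 = 221.2, rounded up to 222.

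Keeping the 25% in the analysis as non-adherent does not give 188. The required N is 167 if 25% of treated women stop over the study, 198 if 25% switch in both arms, 251 if 25% are non-adherent from the start, and 263 if 25% stop per year.

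**2. Keep the non-adherent women.** Let d be the proportion lost and f the non-adherent share of the CE women analysed.
- CE success S = (1 − f) × 0.80 + f × 0.65
- HR = ln S / ln 0.65
- Events D = 188(1 − d) × [0.635 + (1 − f) × 0.417 + f × 0.635]/2

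Example with d = 0 and f = 0.25: S = 0.7625, HR = 0.629, D = 104, power 66% (Schoenfeld) or 68% (Lakatos).

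| Loss / non-adherence | HR | Events | Schoenfeld | Lakatos |
|---|---|---|---|---|
| 25% / 0% | 0.518 | 74.2 | 80.9% | 80.0% |
| 20% / 5% | 0.540 | 79.9 | 78.7% | 78.5% |
| 15% / 10% | 0.562 | 85.8 | 76.1% | 76.5% |
| 12.5% / 12.5% | 0.573 | 88.8 | 74.6% | 75.4% |
| 10% / 15% | 0.584 | 91.8 | 73.1% | 74.2% |
| 0% / 25% | 0.629 | 104.0 | 65.6% | 68.0% |

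The extra events from retained women are counted, and they offset only part of the dilution. If the non-adherent percentage refers to all 188 women, the share among those kept is f/(1 − d), and Schoenfeld power is 1 to 2 points lower: 74.2% for 15%/10% (0.10/0.85 = 0.118, HR 0.570) and 71.2% for 10%/15% (0.15/0.90 = 0.167, HR 0.592). A simulation of the logrank test gave 73–75% for 10%/15%.

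**3. Let non-adherent women keep part of the benefit.** Give them a hazard ratio of 0.518^r. At r = 0.4 this is 0.769, with 1-year success 0.65^0.769 = 0.718. If all 25% are non-adherent, S = 0.75 × 0.80 + 0.25 × 0.718 = 0.7795, HR = 0.578, D = 101.9 and power is 79.0% (Schoenfeld). The 10%/15% split gives 80.3%. At r = 0.5 all splits give 80% or more by either method. Break-even is at about 40–45% of the log hazard ratio.

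**The case against.** - **How the 25% was applied is an inference.** This stands: Section 9.2 does not say. The inference rests on the exact match in step 1 and on the failure of the retained-non-adherence models to give 188.
- **65% v 80% may already be the effect expected in the groups as randomised.** Section 9.2 does not label it. If it is, no dilution is needed, but non-adherence then has no place in a 25% inflation of N. The wording needs correcting either way.
- **Some non-adherence is true loss.** This stands in part. Section 6.2.4 allows withdrawal for non-adherence, and those women leave follow-up. Section 8 keeps the others.
- **Non-adherent need not mean untreated.** This stands. Under the strict definition in Section 5.4 a woman using 75% of her doses is non-adherent; under the second definition 50% of doses is enough. Section 9.2 does not say which applies, and with enough retained benefit the stated 80% holds.

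A reader might go further and apply the pilot's 31% (4 of 13) to the whole trial, concluding that power is close to a coin toss. The documents do not support that: the figure comes from 13 women over six weeks of preoperative use, and with any realistic loss added it exceeds the plan's own 25%. The cited one-year figure of 9.8% corresponds to power of about 76% when the rest of the 25% is lost and non-adherent women get no benefit. Nor do the documents support a single replacement power, because neither the split nor the retained benefit is given.

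**Conclusion.** The point holds in conditional form and is a should-fix. The arithmetic behind 188 and 222 reproduces; what fails is the statement that 188 allows for non-adherence in the analysis that will be run. With no benefit in non-adherent women, the shortfall is 1 to 2 points if nearly all of the 25% is loss and 12 to 14 points if all of it is non-adherence. It vanishes if those women retain about 40–45% or more of the log hazard ratio benefit.

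A reader might infer that the trial is certainly underpowered for this reason, or that 222 must rise. Neither follows.

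These sizes depend on 1 to 4 years of follow-up per woman, which is the frame that reproduces 188. The primary endpoint is at 12 months, and the choice of horizon is a separate and larger question. At 12 months with no dilution and no loss, 188 × (0.35 + 0.20)/2 = 51.7 events give about 66% power (Schoenfeld). The direction of the dilution is the same at 12 months, but the percentages in the table do not carry over.

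**What to change.** In Section 9.2:

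- Apply the N/(1 − d) inflation to loss to follow-up only, and delete the claim that 188 covers non-adherence.
- State the assumed split of the 25%, which Section 5.4 adherence definition is meant, and how much of the effect non-adherent women are assumed to keep.
- Say whether 65% v 80% is the full-adherence effect or the effect expected under modified ITT.
- Report the resulting modified ITT hazard ratio and power at the existing 222 as a range over plausible splits and retained effects, computed at the follow-up horizon of the primary endpoint.

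The analysis set, the per-protocol analyses and N = 222 stay as they are. The cost is a rewritten paragraph and a less favourable stated power.
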